The treatment will be discontinued if the patient develops an adverse event (discussed under *6. Safety Management*) that requires the treatment to be stopped or at the participant request. Subjects will be allowed to start and continue conventional medical therapy for the duration of the study, including any pain medications. This will be at the discretion of the treating physician. This will allow us to assess the addition of TEA to conventional care. The TEA intervention will be discontinued if the patient gets admitted to hospital or if a surgical or endoscopic procedure is performed during the treatment phase of the study. During the 4 weeks of treatment, subjects will complete pain diaries through RedCap. This will take 2 minutes for completion.

IV. Monitoring phone calls

To assess any potential problems with the TEA device, we will contact participants via telephone within 72 hours of starting treatment and then weekly at 1 week, 2 weeks, and 3 weeks from treatment initiation.

V. Visit 2 (V2), 4 Weeks from V1

During this follow-up period subjects will complete the same set of surveys that was completed during the first visit to assess pain, quality of life, and anxiety or depression. Subjects will also return the TEA device using their return mailer (provided during or prior to visit 1). In the event the device is broken or non-functional, participants will still be requested to return the device.

VI. Visit 3 (V3), at 8 weeks from V1

After subjects finish treatment (4 weeks from V1), they will continue completing daily pain diaries for additional 4 weeks. During this phase, subjects will not receive device stimulation. At 8 weeks from V1, subjects will be asked to complete the same set of surveys completed during visit 1 and 2. These will be completed via RedCap.

VII. Close-out phone call, at end of trial

At the end of the trial, study subjects who enrolled and received TEA will be reached out via a phone call to assess on global impression and acceptability of the treatment.

Outcomes

Primary outcomes

1. Enrollment feasibility: how many patients with CP who are assessed meet eligibility criteria. In addition, of these, how many provide informed consent. Of those who consent, how many meet criteria to participate after the run-in period. Of those who meet run-in period criteria, how many start the intervention (TEA).

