Procedure									
Eligibility evaluation	x								
Medical history and demographics	x								
Consent	x								
Pain diary (daily average & worse pain, weekly BPI-SF)	x	x					x	x	
Pain assessment (COMPAT-SF, opioids)		x					x	x	
Quality of life (PROMIS-29)		x					x	x	
Anxiety and depression (HADS)		x					x	x	
Adverse events			x	x	x	x	x		
Pancreatitis-related hospital admissions							x	x	
Patient global impression of change (PGIC)									x
Modified abbreviated acceptability rating profile									x

Recruitment

Participants will be identified using different methods. 1) We will use DataDirect to identify potential participants with chronic pancreatitis who do not have major exclusion criteria and who are actively following at the University of Michigan. This will provide a retrospective list of patients with chronic pancreatitis seen at the University of Michigan in the past 1 year. 2) The study coordinator will also identify potential participants from the list of patients scheduled for clinic visits with [name], [name], or other members of the pancreas clinic. This will be done using MiChart. 3) The study investigators (Drs. [name] and [name]) and physician colleagues seeing patients at the Comprehensive Pancreas Program will refer potential subjects to the study team. The research team will review potential study participants' medical history through the electronic medical record (MiChart) to assess patients' eligibility.

Once a subject is identified through any of the above methods, the subject will be contacted by phone using a phone script or approached in person in the outpatient clinic. The study team will follow a script and go through the pre-screen questions. If the patient is determined to be ineligible via the pre-screen questions they will be excluded from the study and logged as contacted by the study team but ineligible to participate. In doubt, the study investigator will

determine eligibility. If the subject meets eligibility criteria, the subject will be invited to participate in the study. If the subject is interested, an informed consent will be given either in person if the subject is in clinic or mailed for review & signature via eConsent or SignNow.

4. Methods: data collection

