All data will be collected using active and passive methods, including patient interviews, physical examinations, and review of electronic medical records. A trained research coordinator will collect data using standardized forms via RedCap. Research coordinators will follow the manual of operations for all study procedures. All forms will include essential instructions and definitions of variables.

A. Pre-screening form: this will include questions on inclusion and exclusion criteria, pertinent for study eligibility. Initial screening will be based on chart review, in person or telephone patient interview, endoscopic results, and radiologic data that are consistent with the study definition of CP. Screening data will be obtained by the research coordinator before enrollment. This is uploaded into section 8-1.8

B. Pain diary: this will be directly completed by patients. Daily pain scores will be recorded during the 2-week run in period. In those patients who are eligible and are started in TEA, patients will complete the pain diary for 4 weeks during the TEA therapy and will continue for 4 weeks after the intervention is over. The patients will report (a) average pain during the last 24 hours using a VAS, (b) maximal pain during the last 24 hours using a VAS, and (c) weekly BPI-SF (only after intervention started). The survey is uploaded into section 29.1.

C. Baseline form: this will include data on demographics, clinical profile of CP, laboratory biomarkers, radiologic findings, and prior therapeutic interventions, all of which will be recorded from the medical records and by patients filling up a survey. In addition, patients will complete a form pertaining to pain, quality of life, anxiety and depression using the instruments described in secondary outcomes.

D. First follow-up form: this form will be used to assess pain, quality of life, anxiety and depression after the intervention, using the instruments described in secondary outcomes. Adverse events of the intervention will also be recorded in this form. These surveys are uploaded into section 29.1.

E. Second follow-up form: This form will be given to participants during the first follow-up (V2). Subjects will be asked to complete and mail the follow-up questionnaires and diary. This form will be used to assess pain, quality of life, anxiety and depression after the intervention has been discontinued. These surveys are uploaded into section 29.1.

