- Proportion of approached participants who meet eligibility criteria.
- Proportion of those who meet eligibility criteria and who provide informed consent
- Proportion of participants who meet the criteria after the run-in period among those who provided informed consent.
- Proportion of participants who start the intervention among those who meet run-in period criteria.

- B. Adherence: proportion of participants who adhere to the intervention as prescribed among those who start the intervention
- C. Retention feasibility: proportion of patients who complete follow up visit at 4 weeks and return complete follow-up questionnaires at week 8, among those who started the intervention
- D. Visit duration:
 - For visit 1, median (IQR) of the time that takes to complete visit 1.
 - For visit 2, the median (IQR) of the time that takes to complete visit 2.
- E. Data collection feasibility:
 - Proportion of participants who come for visit 1 and complete all the surveys involved in the study.
 - Proportion of study surveys that are completed per protocol

Exploratory endpoints

- Worst pain on visual analogue scale
 - Mean \pm SD of worst pain during the run-in period (baseline)
 - Mean \pm SD of worst pain during the treatment period (week 0-4)
 - Mean \pm SD of worst pain during the last week of treatment (week 4)
 - Mean \pm SD of worst pain after completion of treatment (week 5-8)
 - Mean \pm SD of worst pain during the last week without treatment (week 8)
 - Mean difference of worst pain score from the last week of treatment compared to baseline worst pain.
 - Rank-sum test or paired t test depending on data distribution to compare worst pain score from the last week of treatment compared to baseline worst pain.
 - Mean difference of worst pain score after completion of treatment compared to worst pain during the last week of treatment
 - Rank-sum test or paired t test depending on data distribution to compare worst pain score after completion of treatment compared to pain severity from the last week of treatment.
- Average pain on visual analogue scale
 - Mean \pm SD of average pain during the run-in period (baseline)
 - Mean \pm SD of average pain during the treatment period (week 0-4)
 - Mean \pm SD of average pain during the last week of treatment (week 4)
 - Mean \pm SD of average pain after completion of treatment (week 5-8)
 - Mean \pm SD of average pain during the last week without treatment (week 8)

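### Does it matter that the first enrollment-feasibility proportion is worded over assessed patients in one section and approached patients in another?

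*Combined protocol and SAP*

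**What the plan says.** Two places in the combined protocol and SAP describe the same quantity.

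- Section 3, Outcomes, primary outcome 1, asks "how many patients with CP who are assessed meet eligibility criteria".
- Section 5, Primary outcomes, A. Enrollment feasibility, lists "Proportion of approached participants who meet eligibility criteria".

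The steps around it are described elsewhere.

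- Section 3, Recruitment, begins with a database search "to identify potential participants with chronic pancreatitis who do not have major exclusion criteria", alongside clinic lists and physician referral. It then has the team review each candidate's "medical history through the electronic medical record (MiChart) to assess" eligibility.
- The next paragraph there says: "Once a subject is identified through any of the above methods, the subject will be contacted by phone", or else met in clinic. Those found ineligible on the pre-screen questions are "logged as contacted by the study team but ineligible to participate".
- Section 4, item A (pre-screening form), says "Initial screening will be based on chart review, in person or telephone patient interview", together with endoscopic and radiologic results.

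Section 5 summarizes all primary outcomes descriptively, as counts with percentages or as means or medians. The planned size is 10 subjects who receive the device.

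**The concern.** A proportion needs one denominator, and here two words are used for it. The difference stands out because the later enrollment steps (consent, run-in, start of treatment) correspond between the two sections.

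The words need not mean the same thing. Chart review can assess a patient without any contact, so a patient excluded at that point would count under Section 3 but not under Section 5. The only other use of *approached* is in "contacted by phone using a phone script or approached in person in the outpatient clinic", where it is set beside phone contact; read literally, Section 5 might leave out patients reached by phone. A patient who passes chart review but is never reached has unknown eligibility, and neither section says how to count that patient.

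At stake is the eligibility rate carried forward to the larger trial. Assessing enrollment methods is a stated aim, and this is the first step of the first primary outcome. A rate among approached patients does not by itself show how many charts must be screened to find one eligible patient.

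**Working it through.** **No figure to reproduce.** The documents state no eligibility rate, screening count or feasibility threshold, and the sample size of 10 comes from no formula. The check is therefore textual, with arithmetic only to show how far the two readings could part.

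**Do the documents show two different groups?**

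1. The only removal before contact that is stated outright is the database filter. It acts on how candidates are found, before anyone is assessed individually, so it affects neither denominator.
2. Chart review is described as assessing eligibility, but no sentence says that patients are dropped at that point. The text that follows sends identified subjects on to contact.
3. The one exclusion described in Recruitment comes after the pre-screen questions, and it is logged.
4. Exclusions 8 (prolonged daily opioid use) and 9 (illicit drug use) are self-reported. Full assessment therefore requires speaking to the patient, so *assessed* and *approached* can describe the same people.
5. Phone contact and clinic approach are two routes of first contact in one sentence. Confining *approached* to the clinic would discard everyone phoned, and nothing suggests that this is intended.

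**How large could the difference be if the groups do differ?** Let A assessed = C excluded on chart review + U not reached + P approached. Let E be the number eligible among P, and q the share of U who are truly eligible.

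- Section 5 version: E/P.
- Section 3 version: (E + qU)/A.

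If U = 0 and everyone excluded is ineligible, the ratio of the first to the second is A/P = 1/(1-r), with r = C/A.

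| r (assumed) | Ratio |
|---|---|
| 0 | 1.00 |
| 10% | 1/0.90 = 1.11 |
| 25% | 1/0.75 = 1.33 |
| 50% | 1/0.50 = 2.00 |

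With patients not reached (all counts assumed, A = 100, P = 50, E = 30):

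- C = 40, U = 10: Section 5 gives 30/50 = 60%. Section 3 gives 30/100 = 30% if q = 0, and 40/100 = 40% if q = 1.
- C = 0, U = 50: Section 5 again gives 60%. Section 3 gives 30/100 = 30% if q = 0, and 80/100 = 80% if q = 1.

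The last range comes entirely from unknown eligibility among patients not reached. It would remain if both sections said *assessed*, so it does not measure the mismatch.

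**The case for a change.** The strongest case for a change is this. Feasibility proportions are the primary results of this study, and they are meant to shape a randomized trial. Section 4 promises forms with variable definitions and a manual of operations, but a form cannot decide which of two protocol wordings is the outcome. The only log described is of patients who were contacted, so a count of chart exclusions is not assured, and counts not kept during screening may be hard to recover. The remedy would be a few lines of text.

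Part of this stands. The two sections do use different words, both are current text, and nothing visible reconciles them. A reader of the results will want to know which patients form the denominator.

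The rest does not amount to a defect. The pre-screening form covers chart review as well as interview, so the plan already has a place to record either outcome. Keeping separate counts for each screening stage is good reporting practice, but its absence from the text does not make the Section 5 proportion wrong.

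One might add that the clinic volume in Section 8 (314/3, roughly 104 new patients a year; 104 x 0.87 = 90.5 with pain) cannot be multiplied by a rate among approached patients. The protocol never makes that calculation. The volume also omits return patients, who are a recruitment source, and a rate among assessed patients would not apply to it directly either, because the database filter comes first.

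**Conclusion.** No change to the plan follows. This is a loose choice of words that leaves a gap analysts can fill sensibly. Followed as written, Section 5 yields a valid conditional rate: of the patients contacted, how many were eligible. It is reported with its numerator and denominator, so readers can see what was divided by what.

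The effect on the reported proportion may be zero, and the documents do not show that it is anything else. It becomes material only if a sizeable share of patients is dropped on chart review without contact; at an assumed 25% the two proportions would differ by a factor of 1.33. Even then, no hypothesis test, power figure, sample size or progression rule would move.

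The conclusion rests on two readings: that *approached* covers both phone and clinic contact, and that complete assessment includes the pre-screen questions. The Recruitment text and the self-reported exclusions support both. Using one term in both sections would be tidier, but it is optional.

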Approach: We propose to conduct an open-label feasibility trial to understand the feasibility of TEA in patients with painful CP. In this open-label study, all subjects will receive TEA at acupoint ST36 in an unblinded manner. This will inform on recruitment & retention rates, percentage of patients with complete data collection and compliance with study procedures. This will also assist in sample size calculations for a future larger study.

Aim 2: To collect pilot data on the efficacy of TEA on abdominal pain, patient reported outcomes, and quality of life, in patients with painful CP. TEA at ST36 has been shown to be effective in the treatment of patients with abdominal pain due to visceral hypersensitivity and pancreatic inflammation.^{10, 15} We will use parameter P100 (100Hz, 0.5ms, 0.1s-on and 0.4s-off, and tolerable current output), which has been found most effective in treating visceral pain in animals and patients with irritable bowel syndrome.^{13, 16} TEA at this acupoint may be effective in ameliorating pain in CP by improving pancreatic inflammation or autonomic function.

3. Methods: participants, interventions, and outcomes

In this study, we aim to assess feasibility of TEA, enrollment methods, and data collection tools. All patients will receive TEA via ST36 twice daily (a point below the knee cap) in an unblinded fashion. We will then use this preliminary data to apply for competitive funding to conduct a larger study. The population, intervention and outcome for this study are summarized in **Table 1**.

Table 1: Summary of study population, interventions, outcomes and setting

Population	Adult subjects aged 18 to 75 years with chronic pancreatitis and abdominal pain
Intervention	Home-based 30-minute sessions of TEA twice a day for 4 weeks
Control	None
Outcome	Enrollment, retention, and data collection feasibility
Setting	Comprehensive pancreas clinic at the University of Michigan

Eligibility criteria:

Inclusion criteria

1. Age 18 to 75 years of age.
2. Diagnosis of chronic pancreatitis, based on a score ≥ 4 using the previously validated Mayo scoring system that uses morphologic and functional criteria¹⁷, or endosonographic features suggestive or consistent with CP based on Rosemont criteria¹⁸.
3. Abdominal pain present at least once a week within the last month
4. Willing and able to provide written informed consent

Exclusion criteria

1. Pregnancy or breastfeeding mother
2. Imprisoned individuals

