In this initial visit, subjects will complete baseline questionnaires. This visit will either be in-person at the main hospital in Ann Arbor or performed remotely with the study coordinator. After enrolling in the study, subjects will be given the TEA device and receive instructions on how to use this via ST36. If the participant chooses to have the visit be remote, they will receive the study materials by mail prior to the visit and a pregnancy test supplied by the study team. In

either method of visit, the participant will be given a paid return mailer to give our supplies back. Participants will be subjected to a pregnancy test if they are of child-bearing potential on the day of V1. This will be done in the clinic or self-administered by the subject at home prior to the Zoom appointment. Recommendation to use some form of contraception during the study and birth control options will be discussed. Study participants will use the TEA device for 5 minutes under the supervision of the study coordinator. Subjects will be asked to start the intervention one day after the training received during the initial visit.

III. Home-based treatment period- 4 weeks

TEA will be self-administered at home over two daily treatment sessions of 30 minutes each. TEA will be performed using a device that measures about 4x6 cm (**Figure 2**), and that is programmed by the study team to deliver a specified weak electrical signal. The subject is able to adjust the stimulation output by pressing the “+” or “-“ sign on the device. The stimulation output is adjustable, because the tolerance level varies by individuals and settings will be adjusted based on maximal tolerance. The maximum current output is 10mA. All other parameters, including frequency, pulse width, and time on/time off during the pulsed stimulation, will be fixed. TEA is similar to a transcutaneous electrical nerve stimulation (TENS) unit that is classified by FDA as a non-significant risk device. The device is powered by a small rechargeable battery and the charging will take place only when the device is not in use. This device has been approved for use in two ongoing clinical studies at UoFM by the same investigation team (HUM00189911, HUM00217301).

[figure not shown]

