TEA will be delivered through stimulation of acupoint ST36, located four subject’s finger widths down from the bottom of the knee cap along the outer boundary of the shin bone (**Figure 3**). TEA will be applied to one leg at a time. Participants may choose to switch legs with each session. Participants will be informed to switch legs if any skin irritation occurs. Subjects will be asked to perform the two daily

stimulations at least 6 hours apart but no more than 14 hours apart. This variability in the selected leg or time interval is not expected affect the efficacy of the intervention. Devices will be labeled with unique identifiers and device supply will be tracked upon dispense and retrieval from subjects. For the stimulation of this acupoint, one electrode will be placed right at the acupoint and the other electrode at 3-4 cm below the first electrode along the leg. TEA will be performed using parameter set P100. P100 uses intermittent pulse trains with a train on-time of 0.1s and off-time of 0.4s (2 trains/second), and a pulse frequency of 100Hz and width of 0.5ms within each train, and a sensible but tolerable current output based on the patient’s tolerance (maximal current that the patient can tolerate without feeling discomfort or pain by the current used). Previous studies have shown that EA at 2 Hz accelerates the release of enkephalin, beta-endorphin and endomorphin, while EA at 100 Hz selectively increases the release of dynorphin;

Figure 2: Photo of the existing TEA device

Figure 3: Location of ST36 for TEA

a combination of the two frequencies produces a simultaneous release of all opioid peptides, resulting in a maximal analgesic effect.^{21, 22} In our Parameter set P100, there are two frequency components: 100Hz pulses and 2Hz trains. EA and TEA with this parameter set have been shown to be effective in reducing abdominal pain.^{13, 23, 24} Adherence will be directly monitored through use of the TEA device. The TEA automatically records duration of use, time of the day, and stimulation intensity.

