2. Adherence: of those who start the intervention, how many adhere to the intervention as prescribed. The time of the day and duration of each TEA administration will be automatically recorded by the TEA device.
3. Retention feasibility: how many patients who start the intervention complete follow-up visit at week 4 and return complete follow-up questionnaires at week 8.
4. Visits duration: how long does it take to complete visits 1 and 2.
5. Data collection feasibility: how many patients complete all the surveys. In addition, we will calculate the proportion of study surveys that are completed per protocol

Exploratory outcomes

1. Pain diary records [timeframe: daily from 2-week run-in period until 8 weeks from treatment onset]: this will be used to measure daily pain experience on an 11-point visual analogue scale (VAS). The recording of daily pain scores will be started during the 2-week run-in period and will end 8 weeks after the intervention is over. Subjects will mark a point along a scale (from no pain [0] to worst imaginable pain [10]) on the VAS related to (a) average pain and (b) worst pain during the last 24 hours on two separate entries. This will be done at a fixed time of the day chosen by the participant. We will measure the change of average and worst pain from baseline to 4 weeks and 8 weeks post-treatment.
2. Brief Pain Inventory—Short Form (BPI-SF) [timeframe - weekly from baseline until 8 weeks from treatment onset]: The BPI-SF is a validated self-reported tool that evaluates pain severity and pain interference with daily activities at the time of assessment. A total of 4 pain intensity items (worst, least, average, and current pain) are rated on an 11-point numerical rating scale (0 = no pain, 10 = worst possible pain). The pain interference subscale includes 7 items evaluating the impact of pain on sleep, mood, walking ability, general activity, work, relationships, and enjoyment of life over the past 24 hours rated on an 11-point scale from 0 = does not interfere to 10 = completely interferes. Possible scores for pain severity range from 0 to 40 (higher scores reflect more severe pain); possible scores for pain interference range from 0 to 70 (higher scores reflect more pain interference with daily life).

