All data will then be captured in a password-protected database through Redcap. Several methods will be used to promote data quality and integrity including database development, proper training of study team members, and use of data quality rules and validation. Each subject will be assigned a unique random number, and Protected Health Information will be coded to

ensure no one outside the study team will be able to identify a subject's identity. This database will be stored in a password-protected database, in a password-protected folder on a secure server behind the University of Michigan firewall. The information will, at all times, only be able to be accessed by the study investigators.

F. After enrollment is completed, study subjects who enrolled and received TEA will be reached out via a phone call to assess on global impression and acceptability of the treatment. Study subjects will be asked the following questions in relation to the use of TEA on their chronic pancreatitis pain.

- Patient global impression of change (PGIC): this is a 1-item question that should take less than 1 minute
- Modified abbreviated acceptability rating profile: this is an 8-item questionnaire that should take 2 minutes (Tarnowski KJ, Simonian SJ. Assessing treatment acceptance: the Abbreviated Acceptability Rating Profile. *J Behav Ther Exp Psychiatry* 1992;23:101-6).
- Two open questions: (i)“How did the TEA device help you in managing your pancreatitis pain?” and (ii)“What modifications would you suggest to improve the TEA treatment?”

5. Statistical methods

Sample size calculation

We will conduct an open-label pilot study of 10 subjects with CP that fulfill eligibility criteria and that receive the TEA device during visit 1. This will serve to inform feasibility on enrollment, adherence, retention, and completion of data collection. Data obtained in this study will lead to protocol changes for a larger randomized controlled trial that we will plan in the future. The study will be under powered to address any clinical outcomes. We anticipate attrition of approximately 10% for a study of this nature.

Statistical analysis

All analyses will be performed according to the intention-to-treat principle. All primary outcomes will be measured using descriptive statistics as absolute values (percentage), mean \pm standard deviation (SD), and median (interquartile range [IQR]), as appropriate.

Primary outcomes

A. Enrollment feasibility:

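### Primary adherence is planned only as a yes/no share with no cut-off, and no summary of the sessions or minutes delivered is planned although the device logs them

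*Combined protocol and SAP*

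**What the plan says.** Adherence is one of five primary outcomes. Section 3 (Primary outcomes, 2) asks, "of those who start the intervention, how many adhere to the intervention as prescribed", and adds: "The time of the day and duration of each TEA administration will be automatically recorded by the TEA device". Section 5 (Primary outcomes, B) makes the statistic the "proportion of participants who adhere to the intervention as prescribed among those who start the intervention".

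The regimen is stated in Table 1: "Home-based 30-minute sessions of TEA twice a day for 4 weeks". Section 3, III asks for the two daily "stimulations at least 6 hours apart but no more than 14 hours apart".

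The opening of the statistical analysis section says "All analyses will be performed according to the intention-to-treat principle" and allows counts with percentages, mean (SD) or median (IQR) for the primary outcomes. It does not name an adherence quantity to which a mean or median would apply. Other primary outcomes are spelled out further. Visit duration (D) has a median (IQR). Data collection (E) has a share of participants and also an item-level share: "Proportion of study surveys that are completed per protocol". Adherence has the participant-level share alone.

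**The concern.** Two things are missing: the rule that makes a participant adherent, and any planned measure of how much treatment was delivered.

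The study is a 10-person pilot whose stated purpose is to inform feasibility, adherence included, and to shape a larger randomized trial. The planners of that trial need to know how much TEA people deliver at home. A yes/no share mixes the amount delivered with the way misses are spread over participants, and with ten people each one moves it by 10 percentage points. If no cut-off is written down before the logs are examined, the reported figure also depends on a definition that could be chosen with the data in view.

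A related gap concerns participants whose treatment is stopped under the protocol's own rules (section 3, III: hospital admission, a surgical or endoscopic procedure, or an adverse event; section 6: a serious adverse event). They remain in the denominator of starters, but the plan does not say how they count.

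**Working it through.** The plan states no adherence target, expected rate or precision, so there is no figure of its own to reproduce. The check asks what the planned share would show.

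**Inputs from the documents.** Two 30-minute sessions a day for 4 weeks (Table 1); 10 participants receiving the device and about 10% attrition (section 5, sample size). Treatment starts after the training visit: "Subjects will be asked to start the intervention one day after the training received during the initial visit".

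- Sessions prescribed per participant: 2 × 28 = 56
- Minutes prescribed per participant: 56 × 30 = 1,680
- Sessions prescribed over ten participants: 10 × 56 = 560

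**Step 1. Literal reading: adherent means 56 of 56. No model is needed.**

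| Pattern | Delivered | Adherent |
|---|---|---|
| Nine at 56, one stops at 28 | (504 + 28)/560 = 532/560 = 95.0% | 9/10 |
| Eight at 53, two at 54 | (424 + 108)/560 = 532/560 = 95.0% | 0/10 |
| Ten at 28 | 280/560 = 50.0% | 0/10 |

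The first two rows have the same delivery and opposite results. The last two have very different delivery and the same result. The first row has one early stopper in ten, in line with the plan's own attrition figure.

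**Step 2. A looser cut-off is meant, but it is not stated.** The assumptions here are mine: a session completion probability p of 0.90 or 0.95; cut-offs of 56, at least 51 (51/56 = 91%) and at least 45 (45/56 = 80%); and a within-participant correlation ρ from 0 to 0.30. The documents give none of these. With ρ = 0 the number of sessions is binomial(56, p), so P(56) = p^56; for example, 0.90^56 = 0.0027. With ρ > 0 it is beta-binomial with parameters p(1−ρ)/ρ and (1−p)(1−ρ)/ρ; for p = 0.90 and ρ = 0.30 these are 2.1 and 0.233.

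Expected share adherent:

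| p | ρ | 56/56 | ≥51 | ≥45 | Gap between strictest and loosest (points) |
|---|---|---|---|---|---|
| 0.90 | 0 | 0.3% | 51% | 99% | 99 |
| 0.90 | 0.05 | 7% | 57% | 90% | 83 |
| 0.90 | 0.30 | 44% | 71% | 83% | 38 |
| 0.95 | 0 | 6% | 94% | 100% | 94 |
| 0.95 | 0.05 | 26% | 84% | 98% | 72 |
| 0.95 | 0.30 | 67% | 85% | 92% | 25 |

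The gap narrows as misses cluster within people, but it is still 25 to 38 points at ρ = 0.30.

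**Step 3. Does the proposed summary avoid the problem?** Every starter has the same denominator of 56, so the pooled percentage equals the mean of the individual percentages. It is 95.0% for both of the first two patterns in step 1 and 50.0% for the third. A median (IQR) alone would not be enough: nine at 56 and one at 28 gives a median of 100% with IQR 100% to 100%, which hides the early stopper. Individual values and the range (50% to 100%) show that person.

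**The case against.** The strongest reply is that the prescription is fully specified in sessions, length and spacing, so adhering to it is already defined. The general sentence on descriptive statistics permits a mean or median. Section 4 says that forms will define their variables and that a manual of operations exists. The logs carry time stamps, so sessions and minutes could be reported later without loss. The study is descriptive, with no adherence test, target or progression rule, so no error rate is at risk.

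Part of this stands. It limits the consequence, and the cut-off figures in step 2 rest on assumed rates and correlations. It does not supply what is missing. If the literal rule is intended, step 1 shows that it cannot describe delivery. If it is not, the cut-off is absent. Permission to use a mean is not a plan to use one, and the manual is not among the documents.

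Three stronger readings are tempting, and the documents do not support them.

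- **The share would rank high delivery below low delivery.** Ten at 55/56 (98.2%) give 0/10, while five at 56 and five at 1 (285/560 = 50.9%) give 5/10. This needs the literal rule; at 51 or 45 sessions the results are 10/10 and 5/10, in the expected order. It also needs half the sample to stop after one session, against about 10% attrition anticipated.
- **The one-week window for visit 2 would inflate delivery.** Section 3, VI has treatment finishing 4 weeks from visit 1, with no stimulation afterwards. The window in Table 2 applies to the visit. Inflation would need use outside the protocol that is also counted.
- **The session spacing is optional.** The remark in section 3, III that variability in the interval should not affect efficacy follows the 6 to 14 hour instruction and most naturally means variation within that range. What is unstated is whether keeping to the spacing counts toward adherence.

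**Conclusion.** The concern holds. As written, a primary outcome of this pilot is a single yes/no share with no cut-off, and no planned statistic shows how much TEA was delivered. Under the literal rule, 95.0% delivery can read as 9/10 or 0/10; this is arithmetic and rests on no model. Under an unstated looser rule, the expected share moves by 25 to 99 points between the strictest and loosest cut-offs considered, across the assumed completion rates of 90% to 95% and correlations of 0 to 0.30. The upper end belongs to independent misses and should not be taken as typical.

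This should be corrected, but it is not a serious flaw: safety, sample size and hypothesis tests are unaffected, and the data needed are already being collected.

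**What to change.** In section 5, Primary outcomes, B:

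1. Make the primary adherence summary the device-recorded sessions and minutes delivered in the 4-week treatment period, as a percentage of the 56 sessions and 1,680 minutes prescribed, for all starters. Give the mean (pooled) percentage, each participant's value, and the median and range.
2. Label this as treatment delivered. List separately, with reasons, participants whose treatment was stopped under the protocol's own rules (section 3, III and section 6), so that stopping directed by the protocol is not read as non-adherence.
3. Keep the yes/no share as a second line. Before the logs are examined, fix its session cut-off and state whether the 6 to 14 hour spacing counts.

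The cost is a change of wording and a few added descriptive lines. No new data are needed, and no test or sample size changes. The small downside is that a cut-off has to be chosen, and defended, in advance.
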